6.1 Statistical power and sample size considerations

The pilot RCT will enroll 60 participants (30 EMPOWER, 30 enhanced usual care). This number of participants ensures stable estimates of treatment effects and confidence intervals, and, in case the effects of EMPOWER happen to be large, adequate (~80%) statistical power to detect a minimum treatment effect size (Cohen's d) of 0.75 (at alpha=0.05).

Of note, participants from the COVID-19 open trial will be considered in this N of 60. Accounting for these participants, the projected balance between groups will be 2:1, or 40 EMPOWER participants to 20 EUC. At 80% statistical power and alpha=0.05, this assignment ratio is still sufficient to detect a minimum treatment effect size (Cohen's d) of 0.75.

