This trial initially proposed to have 15 eligible stakeholders provide feedback about EMPOWER to inform improvements; to enroll 10 initial open trial cases and then to randomize 60 surrogate decision-makers of terminally, critically ill patients who are incapacitated or at risk of becoming incapacitated to EMPOWER or enhanced usual care. Beginning in April 2020, however, to meet the needs of family members in the COVID-19 pandemic, as well as to accommodate recruitment of human subjects with necessary social distancing practices, the RCT phase was paused to enter a new open trial phase (referred to hereafter as the COVID-19 open trial) that did not include randomization or a control arm. Upon approval of amendment #1610017622-13, we will return to the RCT phase. To adhere to recruitment strategies that were originally proposed, the number of participants enrolled in this study will not exceed the 60 participants initially projected, although due to the COVID-19 open trial, over 30 participants total may receive the EMPOWER intervention. Assessments will occur pre-intervention, immediately post-intervention, and then 1 month and 3 months from post-intervention assessment. Results will be used to seek NIH R01 funding for a larger-scale randomized controlled trial (RCT) intervention efficacy study of EMPOWER.

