1.1 Overview

To obtain stakeholder input on EMPOWER and refine the intervention manual, we propose to enroll up to 10 bereaved caregivers of patients who were incapacitated and treated in the ICU and 10 clinicians with expertise in ICU and/ or mental health care to have them review the study protocol and intervention manual and to obtain structured feedback on EMPOWER. Interviews will be audio-recorded, transcribed verbatim by trained staff, and kept confidential. Participants will also have the option to respond to interview questions through written response. In addition, we will enroll family caregivers and ICU patients to pilot the EMPOWER intervention and examine its effects on both informal caregivers and patients in the ICUs at New York Presbyterian Hospital (NYPH)- Weill Cornell, New York Presbyterian Hospital-Queens, and Memorial Sloan Kettering Cancer Center (MSK), as well as among surrogate decision-makers from outside hospitals recruited online. Surrogate decision-makers will be screened for emotional dependency on the patient and feelings of emotional distress related to the patients' ICU admission. Eligible surrogate decision-makers will be enrolled. The first 10 surrogate decision-makers will be enrolled in an open trial. A pilot RCT will then begin, randomizing surrogate decision-makers to receive either EMPOWER or enhanced usual care using a block-randomization strategy to determine condition assignment., A second open trial phase, only assigning surrogates to the EMPOWER trial in response to the COVID-19 pandemic, began on April 2020, with a return to the RCT following approval of amendment #1610017622-13. 60 surrogate decision makers will be enrolled in the RCT and COVID-19 open trial phases combined. Surrogate decision-makers will be assessed at 4 time points (T1 = baseline, T2 = up to one week following intervention, T3 = one month from T2, and T4 = three months from T2). The EMPOWER intervention will be administered by trained interventionists either in-person or via telehealth. The intervention sessions will be audio-recorded for training purposes. If participants agree, the sessions will be video-recorded. Patients' medical chart information will be abstracted

following the death of the patient. If the patient is not deceased by the end of their surrogate decision-maker's participation in the study, medical chart information will be abstracted at T4.

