2.0 Objectives

Specific Aim #1:

Develop EMPOWER for surrogate decision-makers of critically ill ICU patients who are at risk of becoming incapacitated and/or who are currently unable to make medical decisions.

There are no hypotheses for this objective. Stakeholders, including bereaved ICU patient caregivers and clinicians, will be asked to evaluate the EMPOWER intervention manual to increase its potential tolerability, acceptability, and efficacy. Data from the open trial of 10 surrogate decision-makers will also identify tactical and measurement issues involved in the delivery and outcome measurements used in EMPOWER.

Specific Aim #2:

Determine feasibility, tolerability, acceptability, and preliminary effects of EMPOWER on surrogate decision-maker mental health.

Hypothesis #2:

Revised EMPOWER will be feasible, tolerable, acceptable. Those who are randomized to EMPOWER will have reduced peritraumatic distress at post-intervention assessment (T2). Those who are randomized to EMPOWER will have reduced symptoms of PTSD, prolonged grief disorder, anxiety, and depression, and less decisional regret and experiential avoidance at one-month and three-month follow up from baseline (T3 and T4).

Specific Aim #3:

Examine the effects of EMPOWER on patient outcomes, including intensity of care and quality of life/quality of

death, in the months following baseline assessment.

Hypothesis #3:

Patients whose surrogate decision-makers receive EMPOWER will have better quality of death (for patients who died), better quality of life (for patients who are still alive) and more value-concordant care compared to those whose surrogate decision-makers receive enhanced usual care at one-month (T3) and three-month (T4) follow up from post-intervention assessment.

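### The power section still gives the pilot RCT 60 randomised participants (30:30, about 80% power), although the 60 includes non-randomised COVID-19 cases; neither the number randomised nor its precision is stated, and the 40:20 power claim is slightly optimistic

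*Combined protocol and SAP*

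**What the plan says.** Section 6.1, Statistical power and sample size considerations, opens with "The pilot RCT will enroll 60 participants (30 EMPOWER, 30 enhanced usual care". It credits that number with stable effect estimates and "adequate (~80%) statistical power to detect a minimum treatment effect size (Cohen's d) of 0.75 (at alpha=0.05".

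The next paragraph says "Of note, participants from the COVID-19 open trial will be considered in this N of 60", that "the projected balance between groups will be 2:1, or 40 EMPOWER participants to 20 EUC", and then: "At 80% statistical power and alpha=0.05, this assignment ratio is still sufficient to detect a minimum treatment effect size (Cohen's d) of 0.75".

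Three other sections bear on the meaning of the 60:
- Section 1.1 Overview: "60 surrogate decision makers will be enrolled in the RCT and COVID-19 open trial phases combined". Section 5.2 Study Design (Pilot Trials) agrees: 10 in the initial open trial plus 60 across the RCT and the COVID-19 open trial.
- Section 1.1 Introduction describes the added phase as "referred to hereafter as the COVID-19 open trial) that did not include randomization or a control arm". It caps enrolment at the 60 first projected and warns that more than 30 people may receive EMPOWER.
- Section 2.0 Objectives, Hypothesis #2: "Those who are randomized to EMPOWER will have reduced peritraumatic distress at post-intervention assessment (T2".

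Section 6.1 Data Analysis Plan estimates preliminary effects in the two phases combined. No section gives the number randomised, the number of COVID-19 open-trial cases, or the allocation ratio of the blocks.

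**The concern.** The two paragraphs of the power section describe different studies. The opening sentence describes a randomised trial of 60 in equal arms. The following paragraph describes 60 people from two phases, one of them unrandomised and without controls. Every COVID-19 case counted towards the cap removes one place from the RCT, so both descriptions cannot hold. The second paragraph changes only the arm split of the mixed sample. It calls 2:1 an assignment ratio, but the imbalance comes from adding EMPOWER cases that were never assigned by randomisation.

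This matters because the pilot's effect estimate is an output in its own right. Section 5.2 Study Design says it will help plan a larger efficacy RCT, the Data Analysis Plan says the model supplies the effect size for that study, and the Introduction says the results will support an R01 application. Anyone weighing that estimate needs to know how many people were randomised and how precise that part of the evidence is. The section does not tell them.

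**Working it through.** **Inputs.** d = 0.75, alpha = 0.05, 80% power, 30:30, 40:20 and the combined total of 60 come from the power section and the Overview. Sidedness is not stated. No dropout or clustering allowance is given, and none is applied below unless noted.

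**Formulas.** For arms n1 and n2 with SD = 1:
- SE = sqrt(1/n1 + 1/n2)
- noncentrality = d / SE
- power from the noncentral t distribution with n1 + n2 − 2 df; normal approximation Φ(d/SE − 1.960)
- 95% CI half-width = t(0.975, df) × SE

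**Step 1: reproduce the plan's figure (30:30).** SE = sqrt(2/30) = 0.258; noncentrality = 0.75/0.258 = 2.90. Two-sided power is 81.5% (t) or 82.8% (normal), which matches about 80%. One-sided would be 89.0% (t), so the plan's figure is two-sided. Half-width = 2.002 × 0.258 = 0.52 SD.

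**Step 2: the planned combined comparison (40:20).** SE = sqrt(1/40 + 1/20) = sqrt(0.075) = 0.274; noncentrality = 0.75/0.274 = 2.74. Half-width = 2.002 × 0.274 = 0.55 SD.

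**Step 3: the number randomised.** If C open-trial cases count towards the cap, the RCT has 60 − C people, which is 60 only when C = 0. Assume 1:1 allocation, as 30:30 suggests. All EUC participants come from the RCT, so 20 EUC implies about 20 randomised to EMPOWER and about 40 randomised in all. Then C = 60 − 40 = 20, and EMPOWER totals 20 + 20 = 40, which agrees with the projection.

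**Step 4: the randomised participants alone (20:20).** SE = sqrt(2/20) = 0.316; noncentrality = 0.75/0.316 = 2.37. Half-width = 2.024 × 0.316 = 0.64 SD.

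| Comparison | Power at d = 0.75, t (normal) | d for 80% power, t (normal) | 95% CI half-width |
|---|---|---|---|
| 30:30, as stated for the RCT | 81.5% (82.8%) | 0.74 (0.72) | 0.52 SD |
| 40:20, planned combined sample | 76.8% (78.2%) | 0.78 (0.77) | 0.55 SD |
| 20:20, randomised only (assumed split) | 63.7% (66.0%) | 0.91 (0.89) | 0.64 SD |

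**Step 5: sensitivity.** Two-sided t-test power for the randomised participants alone, 1:1, by number per arm: 15 gives 50.9%, 18 gives 58.9%, 22 gives 68.1% and 25 gives 73.8%. None reaches 80%. With an assumed 10% loss, 40:20 falls to 72.2% and 20:20 to 58.9%.

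**The case against.** The strongest reply is that the section corrects itself. The paragraph straight after the 30:30 sentence says that COVID-19 cases are counted, gives the 40:20 projection and restates power. The Introduction and Overview say the same about the 60. This stands: the change is disclosed, and the fault is an unreconciled sentence plus a missing figure.

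A second reply concerns which comparison the power belongs to. A reader might infer that the trial's power is really 64% and not 80%. The documents do not support that. The Data Analysis Plan specifies the combined sample, for which simple two-group power is about 77%, close to the claim. The randomised-only figure belongs to an analysis that the plan does not contain. Section 5.2 Study Design also states the primary hypothesis in terms of who receives EMPOWER, which fits the combined analysis better than Hypothesis #2 does. This also stands, so the 64% must not be presented as the power of the planned model.

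Third, 20:20 is inferred, because neither the block ratio nor the number of open-trial cases is given. That is correct. It is why the figure carries a range and why the sponsor should supply the counts.

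Finally, this is a pilot focused on feasibility, and it claims power only should the effect turn out large. That lowers the stakes. It does not make a randomised size of 60 true.

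**Conclusion.** The point holds as an inconsistency in the stated size and a gap in reporting. It is not a miscalculation of the 30:30 figure, which reproduces at 81.5%. The RCT cannot have 60 randomised participants under the combined cap once any COVID-19 case is counted, and nothing in the section describes the randomised participants of Hypothesis #2.

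Against the planned combined comparison the shortfall is small: about 77% against the claimed 80%, with a detectable d of about 0.78 against 0.75. The claim comes within two percentage points only by the normal approximation. For the randomised evidence alone the gap is larger: about 64% power, with an interval about 24% wider than 30:30 would give (0.640/0.517 = 1.24).

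The combined figures rest on a two-sided 5% comparison of means at the projected 40:20, without dropout or clustering. The randomised-only figures rest in addition on 1:1 allocation with about 20 per arm; over 15 to 25 per arm the power runs from 51% to 74%. Two stronger readings are not supported: that the plan conceals the change, and that its planned analysis has 64% power.

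**What to change.** In Section 6.1, Statistical power and sample size considerations:

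1. Replace the 30:30 sentence with a combined total of 60 across the RCT and COVID-19 open-trial phases, projected as 40 EMPOWER and 20 EUC. Remove the 80% claim for a 30:30 RCT.
2. Have the sponsor state the number randomised, or expected to be, and the allocation ratio.
3. For the planned combined comparison, restate power at d = 0.75 as about 77% (two-sided t-test; 78% by normal approximation), with 80% power at d of about 0.78 and a 95% CI half-width of about 0.55 SD, before any allowance for clustering or dropout.
4. Beside it, give the figures for the randomised participants alone: if 1:1 with about 20 per arm, about 64% power at d = 0.75 (51% to 74% for 15 to 25 per arm), 80% power at d of about 0.91, and a half-width of about 0.64 SD. Label these as the precision of the randomised evidence, not of the planned combined model, and update them once the counts in item 2 are known.

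The cost is wording only, with no extra enrolment and no design change. The downside is that the stated power becomes less favourable.

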6.1 Data Analysis Plan

Below are descriptions of the statistical procedures performed to test each of the hypotheses. Participant data will be stored in a locked file cabinet and using a secured REDCap database. Missing data will be estimated using a multiple imputation procedure described by Schafer and Olsen³⁷. There will not be a data monitoring committee due to the trial's relatively short duration and the minimal risks the intervention poses. Trial data will

not be independently audited. An interim analysis of the pilot data will occur to inform the conduct of the randomized control and edits to the EMPOWER manual. Data for participants who come bereaved before the administration of EMPOWER or EUC interventions will be treated as exploratory and analyzed separately.

Specific Aim #1: Develop EMPOWER for surrogate decision-makers of critically ill patients who at risk of becoming unable to communicate and/or are currently are unable to communicate in the ICU.

There are no hypotheses for this aim. We will use thematic content analysis, a well-established, systematic qualitative analysis approach in health research, to identify themes from stakeholder participants' narratives and exit interviews. We will follow Morse's²¹ guidelines for conducting rigorous qualitative research (e.g., audit trail, saturation) using Atlas.ti software. We will independently review each interview transcript as well as qualitative data gathered from manual edits and Delphi survey responses and will synthesize and interpret participants' feedback about the content of the EMPOWER manual.

Specific Aim #2: Determine the feasibility, tolerability, acceptability, and preliminary effects of EMPOWER on surrogate decision-maker mental health.

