We will compute descriptive statistics to characterize the feasibility and acceptability of EMPOWER by examining helpfulness/satisfaction ratings, rates of recruitment, reasons for refusal, and number of modules/booster calls completed. Targets will include completion of 4/6 modules for feasibility and tolerability. Target acceptability will be an average score greater than 3 on the acceptability items in the post-intervention satisfaction questionnaire among participants who received EMPOWER. Tolerability will also be measured by open ended-responses to qualitative questions asked at T4 regarding negative experiences, emotional difficulties, and perceived costs and benefits of participating in the intervention. Drop-out will not be considered as a metric of tolerability due to the highly stressful and variable circumstances of ICU caregiving, unless participants drop out of the study and specifically express that they consider it to be too distressing. Qualitative data analysis will be used to analyze data from open-ended questions to identify the most helpful components of EMPOWER.

To evaluate the preliminary effects of EMPOWER among participants in the combined RCT and COVID-19 open trial phases, we will use a hierarchical linear modeling (HLM) and an intent-to-treat approach. HLM is statistically appropriate because of the clustering within interventionists and within surrogate decision-makers. HLM will correct for this clustering by modeling interventionists and surrogate decision-makers as random effects, as has been done in prior trials ^{38 39}. This will also provide a treatment assignment model coefficient and effect size estimate for our future, larger study.

HLM modeling will determine differences between surrogate decision-makers and patients assigned to EMPOWER vs. enhanced usual care. The primary outcome is post-intervention (T2) differences in PDI scores. Secondary outcomes are differences in scores on the PGD 12/13 and BEAQ at one-month (T3) and three-month (T4) follow up from T2. Exploratory outcomes are differences in scores on the IES-R, STAI, PHQ-9 and Decision Regret Scale at one-month (T3) and three-month (T4) follow up. HLM models will include covariates, either as fixed-effect or time-varying, if those variables are found to be significantly statistically associated with both intervention assignment and the outcome examined.

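### The stated 80% power assumes 60 independent surrogates all analysed at T2; it makes no allowance for interventionist clustering, separation of the early bereaved or missing scores, and the projected 40:20 split has no margin for them

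*Combined protocol and SAP*

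**What the plan says.** The section on statistical power and sample size starts from an even split: "The pilot RCT will enroll 60 participants (30 EMPOWER, 30 enhanced usual care"). It claims "adequate (~80%) statistical power to detect a minimum treatment effect size (Cohen's d) of 0.75 (at alpha=0.05"). It then counts the COVID-19 open-trial participants within the 60, so that "the projected balance between groups will be 2:1, or 40 EMPOWER participants to 20 EUC", and says that "this assignment ratio is still sufficient to detect a minimum treatment effect size (Cohen's d) of 0.75" at 80% power. It mentions no ICC, design effect, loss rate or exclusion.

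Other sections describe an analysis with a different structure:

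- **Clustering.** The Data Analysis Plan says "HLM is statistically appropriate because of the clustering within interventionists and within surrogate decision-makers" and fits interventionists as random effects. Under Study Design, a single interventionist delivers all modules to a given surrogate. Enhanced usual care consists of information and resource lists, with no interventionist described.
- **Early bereavement.** "Data for participants who come bereaved before the administration of EMPOWER or EUC interventions will be treated as exploratory and analyzed separately".
- **Missing data.** The Data Analysis Plan uses multiple imputation and gives no expected rate.
- **Cap.** The Introduction says "the number of participants enrolled in this study will not exceed the 60 participants initially projected". The Overview confirms that the 60 covers the RCT and the COVID-19 open trial together.

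**The concern.** The power statement and the analysis plan describe different data. One treats 60 surrogates as unrelated and fully observed. The other expects correlation among surrogates treated by the same interventionist, sets some surrogates aside and imputes missing scores. Each of these features lowers the information available for the T2 comparison of the Peritraumatic Distress Inventory (PDI), and the cap means that losses cannot be made good by enrolling beyond 60.

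What is at stake is how the primary result is read. The plan states a hypothesis of a significant T2 difference in the PDI and will use the results to seek funding for a larger trial. If T2 shows no clear difference, a reader who trusts the 80% figure will take that as stronger evidence against an effect of 0.75 SD than the design can provide.

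**Working it through.** **Inputs from the documents.** d = 0.75, alpha = 0.05, N = 60, and splits of 30:30 and 40:20. Sidedness is not stated; two-sided is used because it fits the claim (one-sided gives 89.0% at 30:30).

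**Inputs not in the documents (assumptions).** Number of interventionists k, ICC, and the share not contributing at T2.

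**Method.** Noncentral t, in SD units:

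- variance of the difference = DE/n1 + 1/n2, with n1 = EMPOWER and n2 = enhanced usual care;
- DE = 1 + (m − 1) × ICC, with m = n1/k, applied to the EMPOWER arm only;
- noncentrality = d/√variance, with n1 + n2 − 2 degrees of freedom.

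**Step 1: reproduce the plan's figure.** At 30:30 with DE = 1, the variance is 1/30 + 1/30 = 0.0667 and the noncentrality is 0.75/0.2582 = 2.905. Power is 81.5% (82.8% by the normal approximation). The claim of about 80% is reproduced with 60 independent, analysed people.

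**Step 2: the projected split.** At 40:20 the variance is 1/40 + 1/20 = 0.075 and the noncentrality is 2.739. Power is 76.8% (78.2% by the normal approximation), and 80% needs d = 0.78. Nothing has yet been lost or clustered.

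**Step 3: loss only.**

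| Analysed | Power at d = 0.75 |
|---|---|
| 29:29 | 80.1% |
| 28:28 | 78.7% |
| 27:27 (10% loss) | 77.2% |
| 24:24 (20% loss) | 72.0% |
| 36:18 (10% loss) | 72.2% |
| 32:16 (20% loss) | 66.9% |

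To have 58 analysed at an even split, 58/0.9 = 64.4, so 65, would have to be enrolled at 10% loss, and 58/0.8 = 72.5, so 73, at 20%. Both exceed 60.

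**Step 4: clustering only, 30:30.**

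- Mild: k = 8, ICC 0.02, DE = 1 + (3.75 − 1) × 0.02 = 1.055, power 80.5%.
- Heavier: k = 3, ICC 0.10, DE = 1 + 9 × 0.10 = 1.90, power 66.0%.

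**Step 5: both together, k = 5, ICC 0.05.** For 36:18, m = 7.2, DE = 1 + 6.2 × 0.05 = 1.31, variance = 1.31/36 + 1/18 = 0.0919 and noncentrality = 2.473. The other rows follow in the same way.

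| Analysed | DE | Power at d = 0.75 | d for 80% power |
|---|---|---|---|
| 27:27 | 1.22 | 72.8% | 0.82 |
| 24:24 | 1.19 | 68.1% | 0.86 |
| 36:18 | 1.31 | 68.0% | 0.87 |
| 32:16 | 1.27 | 63.2% | 0.92 |

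With k = 5, ICC from 0.02 to 0.10 and 10–20% loss, the d needed from an enrolled 40:20 runs from about 0.84 to 0.95.

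**Step 6: what these figures leave out.**

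- *Few clusters.* Full degrees of freedom are optimistic. With k = 4, ICC 0.05 and 36:18, Satterthwaite-type degrees of freedom take power from 66.8% to 61.7%.
- *Baseline adjustment.* Suppose a T1–T2 correlation of 0.5 and multiply the whole variance by 1 − 0.5² = 0.75, which is somewhat generous to the cluster term. Power in the Step 5 cases becomes 84% (27:27), 80% (24:24), 80% (36:18) and 76% (32:16). A correlation of 0.3 restores 80% in none of them.

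**The case against.** The strongest reply is that the 30:30 arithmetic is right and that the documents give nothing from which to size a shortfall. That stands. A reader might infer that the 30:30 figure is wrong, or is certainly not delivered. The documents do not support this: with eight interventionists, ICC 0.02 and no loss, power is still 80.5%. Nor would a design effect on all 60 be justified, since interventionists are described only for EMPOWER.

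A second reply is that the calculation counts what lowers power and omits what could raise it. The PDI is measured at all four time points, so baseline adjustment could recover much of the loss, and imputation from the other time points could recover part of the missing T2 information. Counting every missing score as a total loss is a worst case, and the protocol describes repeat contacts and checks for missing items. This is fair as to size. It does not rescue the statement, because the plan admits covariates only when they are significantly associated with both assignment and outcome, and so does not commit to adjusting for baseline PDI.

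A third reply is that this is a proof-of-concept pilot, where power is mentioned only in case effects prove large and no decision is tied to a null PDI result. That limits the consequence. The section nevertheless states a power for each split, and those figures should match the planned analysis.

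**Conclusion.** The point holds as a matter of unstated assumptions. The claim of about 80% power at a "minimum treatment effect size (Cohen's d) of 0.75" is correct for 60 independent, fully analysed surrogates split evenly, with about two people to spare. It makes no allowance for clustering, separation of the early bereaved or missing T2 scores, all of which the plan itself provides for, under a cap of 60.

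Two results need no assumption beyond a two-sided t-test. The margin at 30:30 is used up by the time 28 per arm remain. The projected 40:20 split gives 77% before anything is lost, although the normal approximation (78%) is closer to the claim. Without baseline adjustment, clustering and loss can only lower these figures; by how much depends on inputs that the documents do not give. The detectable effects of 0.87–0.92 at 40:20 and 0.82–0.86 at 30:30 are illustrations for 5 interventionists, ICC 0.05 and 10–20% not contributing, and are not estimates for this trial. Few-cluster degrees of freedom would raise them; a committed baseline-PDI adjustment or information recovered by imputation would lower them.

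**What to change.** Rewrite the power paragraph and leave enrolment as it is:

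1. Lead with 40:20 and give 30:30 for comparison.
2. Base the power or detectable d on the number expected to contribute to the T2 comparison, after the early bereaved are set apart and with missing scores allowed for.
3. Apply 1 + (m − 1) × ICC to the EMPOWER arm only.
4. State the number of interventionists, the ICC and the loss rate as assumptions, and show a range, for example ICC 0.02–0.10.
5. State the sidedness and the degrees of freedom used, and whether baseline PDI is adjusted for. If credit is taken for that adjustment, the Data Analysis Plan must commit to it in advance.

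The cost is one paragraph of wording and a less favourable stated figure. Nothing in recruitment or trial conduct changes.
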